The M.D. Anderson Symptom Inventory (MDASI) will be used to assess the impact of treatment on symptoms in metastatic BCC patients enrolled after approval of the Study Protocol, version 4.0. For these metastatic patients, incidence and type of disease symptoms will be summarized at baseline. In addition, the number of metastatic BCC patients with 30% reduction in disease-related symptoms with baseline score of 4 or more at any time during treatment will be summarized for each symptom.

Exploratory Pharmacokinetic Assessments

Individual and mean plasma vismodegib concentration versus time data will be tabulated and plotted. Plasma AAG concentration and unbound plasma concentration at selected time points will be estimated, tabulated and summarized (geometric mean, mean, standard deviation, coefficient of variation, median, minimum, and maximum). Additional PK analyses may be conducted as appropriate.

Determination of Sample Size

Approximately 1200 patients will be enrolled in this study.

Synopsis Table 1. Clopper-Pearson 95% Confidence Intervals for the observed AE incidence¹

Number of AE events/ observed AE incidence	95% Clopper Pearson Confidence Interval
12 (1%)	0.5% – 2%
24 (2%)	1.3% – 3.0%
60 (5%)	3.8% – 6.4%
120 (10%)	8.4% – 11.8%
240 (20%)	17.8% – 22.4%
360 (30%)	27.4% – 32.7%

¹ Total number of patients is 1200

Therefore, for a sample size of 1200 patients, the true AE incidence rate can be estimated to within 1.6%–1.8% assuming an observed incidence of 10%, i.e., within 95% Clopper-Pearson confidence interval of 8.4%–11.8%.

Treatment scheme:

[figure not shown]

Table 1 Schedule of Assessments

Cycle	Screening / Baseline	Treatment Phase ¹ (Allowed Visit Window +/- 3 days from Cycle 2 onwards)								End of Treatment Visit ²	Safety Follow-Up Visits ³ (1 month, 3 months, 6 months, 9 months, 12 months after the last dose of vismodegib (GDC-0499))
		1	2	3	4	5	6	7	8 onwards		
Day	-28 to -1	1	29	57	85	113	141	169	Every 28 Days		
Informed Consent ⁴	X										
Archival Tumor Tissue ⁵	X										
Medical History and Demographics ⁶	X										
Complete Physical Examination	X										
Limited Physical Examination ⁷		X	X	X	X	X	X	X	X	X	
Height ⁸ and Weight	X	X	X	X	X	X	X	X	X	X	
Vital Signs ⁹	X	X	X	X	X	X	X	X	X	X	
ECG	X	As clinically indicated								X	
ECOG Performance Status	X	X	X	X	X	X	X	X	X	X	
Hematology	X	X ¹⁰	X	X	X	X	X	X	X	X	X (if clinically indicated)
Biochemistry	X	X ¹⁰	X	X	X	X	X	X	X	X	X (if clinically indicated)

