5.6 DISEASE SYMPTOM ASSESSMENT

The M.D. Anderson Symptom Inventory (MDASI, See [Appendix 6](#)) will be used to assess the impact of treatment on symptoms in patients with metastatic BCC who enrolled after approval of the Study Protocol, version 4.0. Eligible patients will be asked to complete the questionnaire at baseline, i.e., before the start of treatment with vismodegib, at every clinic visit while receiving vismodegib, at the End of Treatment Visit, and at every Safety Follow-Up Visit.

Patients should complete the questionnaire at the beginning of each visit, before any extensive contact and consultation with the clinician/study investigator, as the consultation may bias the patient's perceptions about his or her disease symptom(s).

The MDASI core instrument is a 19-item, valid, and reliable self-report questionnaire ([34](#)) that consists of two scales that assess symptom severity and symptom interference with different aspects of a patient's life. For 13 items (pain, fatigue, nausea, disturbed sleep, distress, shortness of breath, difficulty remembering things, lack of appetite, drowsiness, dry mouth, sadness, vomiting, and numbness or tingling), patients are asked to rate how

severe the symptoms were when “at their worst” in the last 24 hours. For an additional six items, patients are asked to rate how much the symptoms have interfered with six areas of functioning (i.e., general activity, walking, work, mood, relations with other people, and enjoyment of life) in the last 24 hours. In addition to the core set of items in the MDASI, one additional symptom related to metastatic BCC will be included (coughing from the Lung Cancer module). The MDASI items are rated from 0 to 10, with 0 indicating that the symptom is either not present or does not interfere with the patient’s activities and 10 indicating that the symptom is “as bad as you can imagine” or “interfered completely” with the patient’s life.

In metastatic patients (enrolled before approval of the Study Protocol, version 4.0), disease symptoms will be assessed based on a retrospective review. A comparison of concurrent conditions and sites of metastatic disease at baseline will be used to determine disease symptoms related to metastatic disease.

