8.2.3.2 Quality of Life Analyses and Disease Symptoms Assessment

Skindex-16

The effects of skin disease on patient's quality of life (QoL) will be accessed by the Skindex-16 questionnaire. The Skindex-16 includes three domains: symptoms, emotions and function. For ease of interpretation of scores, responses will be transformed to a linear scale of 100 varying from 0 (never bothered, i.e., best) to 100 (always bothers, i.e., worst). Distribution of scores for each domain over time will be presented by box plots and summary tables for continuous variables by means of mean, standard deviation, median, minimum, maximum, and 25th and 75th percentile. The mean scores will be presented by line graphs and corresponding 95% confidence intervals over time. Changes from baseline will be summarized by descriptive statistics and displayed together with associated 95% confidence intervals. Individual items of interest for each domain might also be summarized by frequency tables and presented by bar charts.

M.D. Anderson Symptom Inventory

The MDASI instrument will be used to determine the rate and the number of patients who have a 30% reduction in disease-related symptoms in metastatic BCC patients (e.g. pain, fatigue, shortness of breath, lack of appetite, dry mouth and coughing) following treatment with vismodegib in patients who have at least a score of 4 points at baseline.

QoL will be analyzed for the ITT population. If the safety population differs by more than 5 patients from the ITT population, then some QoL summaries might be presented for the safety population, as well.

More details will be presented in the statistical analysis plan.

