Appendix 6 M.D. Anderson Symptom Inventory (MDASI)

Date: _____

Institution: _____

Participant Initials: _____

Hospital Chart #: _____

Participant Number: _____

M. D. Anderson Symptom Inventory- (MDASI) Core Items

Part I. How severe are your symptoms?

People with cancer frequently have symptoms that are caused by their disease or by their treatment. We ask you to rate how severe the following symptoms have been *in the last 24 hours*. Please fill in the circle below from 0 (symptom has not been present) to 10 (the symptom was as bad as you can imagine it could be) for each item.

	Not Present										As Bad As You Can Imagine	
	0	1	2	3	4	5	6	7	8	9	10	
1. Your pain at its WORST?												
2. Your fatigue (tiredness) at its WORST?												
3. Your nausea at its WORST?												
4. Your disturbed sleep at its WORST?												
5. Your feelings of being distressed (upset) at its WORST?												
6. Your shortness of breath at its WORST?												

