## MDASI Reductions for Patients with Disease Related Symptoms:

The protocol suggests that the MDASI reduction in disease related symptoms should only be considered for patients who had four (or more) MDASI points at baseline, in order to obtain a meaningful assessment of reduction in severity from baseline. It is unclear whether this 4 points would be a patient's average baseline score, or baseline score from any domain. The following output, therefore, was created for all patients with a baseline MDASI, patients with any score of 4 or higher at baseline, and patients with an average baseline score of 4 or higher.

	Metastatic (N=XX)	Total (N=XX)
30% Reduction in Disease Related Symptoms		
n	xx	xx
Yes	xx (xx.x%)	xx (xx.x%)
No	xx (xx.x%)	xx (xx.x%)

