### Programming Note:

1. This output will be repeated for different subsets of patients.
2. MDASI was only collected for Metastatic patients, so only display the Metastatic column.
3. Percentages should be based upon the small n.
4. 30% reductions is any 30% reduction in a given analysis variable. See titles and footnotes in the lopo for these different reduction criteria.
5. N is the number of patients within the specific population.
6. Only include the questions for Disease Related Symptoms.
7. If a subject has had a reduction for the given criteria (see 30% reduction note) then they would appear in 'yes' and not in 'no'.

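### The planned MDASI responder rate counts one unconfirmed 30% fall at any time during treatment, so part of it arises without drug effect and it grows with time on drug

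*Protocol*

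**What the plan says.** The synopsis (Statistical Analyses, Disease Symptoms) defines the summary as "the number of metastatic BCC patients with 30% reduction in disease-related symptoms with baseline score of 4 or more at any time during treatment", separately for each symptom. Protocol 8.2.3.2 keeps the 30% rule "in patients who have at least a score of 4 points at baseline", names no visit, and refers to the SAP for detail.

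The SAP section on MDASI reductions states in its programming notes that "30% reductions is any 30% reduction in a given analysis variable". A patient with a qualifying reduction goes in the Yes row and not in the No row. The same note sends the reader to LoPO titles and footnotes for the different reduction criteria; that list is not among the documents supplied. The output is "created for all patients with a baseline MDASI", and also for "patients with any score of 4 or higher at baseline, and patients with an average baseline score of 4 or higher".

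On measurement, Protocol 5.6 says "The MDASI items are rated from 0 to 10", with severity rated at its worst over the last 24 hours. The questionnaire is completed "at every clinic visit while receiving vismodegib, at the End of Treatment Visit, and at every Safety Follow-Up Visit", and treatment visits are 28 days apart. The SAP's General Considerations take baseline as one record, the most recent before treatment or the one from the day of first dose. The study is non-comparative (Protocol 3.1) and tests no hypothesis (Protocol 8.2). Tumour responses, by contrast, must be confirmed at least 4 weeks later (Protocol 3.1 and 5.3.6).

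**The concern.** A 24-hour symptom rating varies from month to month in a stable patient. If one low reading at any visit makes a responder, each further visit is another chance to qualify, and a patient who stays on drug longer gets more chances. In the sets chosen because a single baseline reading was 4 or more, some of those readings were high by chance and will drift down without treatment. No control arm shows how large this background is.

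Protocol 2.2 lists the impact of vismodegib on disease symptoms in metastatic BCC as a secondary objective, and this is the only MDASI responder summary specified. Its table shell shows counts and percentages only. A Yes rate of a half or more could be read as symptom benefit, although moderately reliable scores could give the same rate with no effect.

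**Working it through.** The documents give no expected MDASI responder rate, sample size or score variability, so there is no planning figure to reproduce. The check asks how many patients with no true change the rule would count.

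**Inputs from the documents.** Integer scores 0-10; baseline of 4 or more; response if a later score is at most 0.7 x baseline; one look per 28 days. Median treatment in the metastatic cohort of the earlier pivotal trial was 10.0 months (Protocol 1.1.2.2), or 10.0 x 30.44 / 28 = about 11 visits. That is a proxy for this study.

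**Assumed inputs.** Item mean 3.5, SD 2.5, reliability (correlation between repeat readings without true change) 0.7, 0.8 or 0.9, and independent visit errors.

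**How far a score must fall.** Baseline 4: 0.7 x 4 = 2.8, so 2 or less. Baseline 5: 3.5, so 3 or less. Baseline 6: 4.2, so 4 or less. From these starting points a 2-point fall is enough.

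**How large ordinary variation is.** Within-patient SD = 2.5 x sqrt(1 - reliability) = 1.37, 1.12 and 0.79. The difference between two readings has SD sqrt(2) times that: 1.94, 1.58 and 1.12. A 2-point fall is therefore 1.0, 1.3 or 1.8 SDs of pure noise.

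**Simulation.** Score = stable true value + visit error, rounded and held to 0-10, with 400,000 patients per setting and no treatment effect. Percentage counted as responders among those with baseline 4 or more:

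| Rule | Reliability 0.7 | 0.8 | 0.9 |
|---|---|---|---|
| Any of 3 visits | 51 | 39 | 21 |
| Any of 6 visits | 66 | 53 | 30 |
| Any of 12 visits | 78 | 66 | 41 |
| One fixed visit | 27 | 20 | 10 |
| Two consecutive of 6 visits | 30 | 21 | 9 |

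Repeat runs agree to about one percentage point. From 3 to 12 visits the rate rises by 78 - 51 = 27, 66 - 39 = 27 and 41 - 21 = 20 points with nothing changing but the number of looks.

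**Which mechanism dominates.** Taking mean 3 and SD 2.5, regression to the mean moves the selected group from 5.35 to 4.63 at reliability 0.7, and from 5.34 to 5.07 at 0.9. With it removed (true baseline 4 to 6), any-of-10-visits noise still gives 50% responders at within-patient SD 1.0, 27% at 0.8 and about 1% at 0.5. Requiring two high baseline readings and using their mean lowers the 10-visit rate at reliability 0.7 only from 78% to 76%. Repeated looks are the larger part.

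**Sensitivity.** With serial correlation of 0.5 between visit errors, the any-visit rates over 3, 6 and 12 visits fall to 28, 43 and 59% at reliability 0.8 and to 13, 23 and 35% at 0.9. With treatment duration drawn around a 10-month median (mean 3, independent errors), reliability 0.9 / 0.8 / 0.7 gives:

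- any visit: 40 / 63 / 74%;
- two consecutive visits: 14 / 30 / 41%;
- Cycle 7 Day 1 with missing counted as non-response: 8 / 16 / 22%.

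**The case against.** The strongest objection is that the size rests wholly on assumed variability. That stands: no item mean, SD or reliability is in the documents, and with within-patient SD near 0.5 the problem almost disappears. Nor need no change be the right reference. Fatigue and lack of appetite are two of the six disease-related items, and the earlier trial reported fatigue in 36% and decreased appetite in 23% of patients on drug. An assumed upward drift of 0.2 points per visit lowers the 6-visit rate at reliability 0.8 from 53% to 34%.

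The plan also has partial safeguards. The SAP's individual-item tables give scores and change from baseline by visit, without the 4-point selection or the any-time rule, though only for patients with measurable disease. The set of all patients with a baseline MDASI avoids selection on a high baseline, though not repeated looks.

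A reader might infer that the SAP itself fixes an any-visit rule. It does not quite: its note speaks of any reduction in a given variable and points to the LoPO, so the explicit any-time wording is the synopsis's. A reader might also count the Safety Follow-Up Visits as extra looks, but the synopsis limits the criterion to treatment.

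Finally, one might add a row for 30% worsening to gauge noise. In patients selected for a baseline of 4 or more it would mislead. With no effect, worsening over 6 visits is about 30-36% against improvement of 53-66% at reliability 0.8 to 0.7. A baseline of 8 would need 1.3 x 8 = 10.4, beyond the scale. The drug would look beneficial by construction.

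**Conclusion.** The concern holds as a matter of definition. The any-time rule is stated, no confirmation or fixed visit appears in the supplied documents, and the resulting rate contains a background that rises with time on treatment. At reliability 0.7 to 0.9 with independent errors, that background is roughly two to three times the fixed-visit rate over 6 visits (66 / 27 = 2.4; 30 / 10 = 3.0). Correlated errors shrink it but do not remove it.

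The documents do not support reading this as showing that vismodegib lacks symptom benefit, or that any observed rate is mostly noise, because the score variability in this population is unknown. The primary safety results and error rates are untouched, since the summary is descriptive and secondary. The harm is to interpretation: the percentage cannot be taken as a treatment effect. If the LoPO already sets a visit or a confirmation rule, the SAP text should say so.

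**What to change.** In the SAP output on MDASI reductions, keep the any-time row as supportive and lead with two rows:

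- (a) a reduction of 30% or more at a fixed scheduled visit, for example Cycle 7 Day 1, showing the number with a score at that visit and counting missing as non-response;
- (b) a reduction of 30% or more held at two consecutive scheduled on-treatment visits.

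Showing the number with a score in (a) matters because counting missing as non-response mixes discontinuation with symptom change. Row (b) still rises somewhat with the number of visits, which is why (a) should stand beside it. Add a footnote that all rates are uncontrolled and, in the sets selected on baseline, include regression to the mean. Cross-refer to the by-visit item tables, and align the LoPO titles and footnotes with the SAP text.

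The data are already being collected. The cost is SAP wording, a few extra table rows and a lower reported responder rate.

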1. BACKGROUND, RATIONALE, AND BENEFIT-RISK

1.1 BACKGROUND

1.1.1 Advanced Basal Cell Carcinoma

Basal cell carcinoma (BCC) is the most common malignancy; for example, of the more than 1 million cases of non-melanoma skin cancer reported in the United States in 2007, approximately 80% are BCC (1-3). Almost all of these cases are small BCCs that can be effectively treated by dermatologists using several surgical modalities. However, in a small subset of patients, invasion of the BCC into subcutaneous structures can occur. In some cases, this results from neglect of indolent BCCs, whereas in other cases patients may develop particularly aggressive BCCs that recur and progress despite standard surgical treatment. If further surgical resection is not possible, there is no approved therapy and no standard of care exists. Although palliative radiation therapy may be used, its use may be limited by the location of the tumor and the involved structures, as well as prior cumulative radiation dosage. Locally advanced BCC can be associated with significant morbidity as the result of chronic pain, risk of bacterial infection and sepsis, bleeding/oozing, and compromise of function, resulting from invasion of structures such as the ear, nose and eye. In some cases, invasion can progress to involve critical organs such as the meninges, brain, and spinal cord, resulting in death (4, 5).

Metastatic BCC is extremely rare, with a reported metastasis rate ranging from 0.0028% to 0.55%; most believe the true metastasis rate to be significantly less than 0.1% (6). A total of approximately 300 cases of metastatic BCC have been reported in the literature. The most common sites of metastasis are the lymph nodes, lung, bone, liver, other viscera, and soft tissue (7). Once metastasis is detected, survival can be short for some patients, with a range of 8 to 14 months reported by some Investigators. However, a 5-year survival rate of approximately 10% has also been reported, and individual patients have been reported to live for as many as 25 years with metastatic disease (8-10). No standard therapy for metastatic BCC exists, although there is anecdotal use of chemotherapeutic agents such as platinum compounds (11).

The Hedgehog (Hh) signaling pathway presents a novel and potentially beneficial target for cancer therapy. Hh signaling regulates epithelial and mesenchymal interactions in a variety of tissues during mammalian embryogenesis (12). The Hh ligand in the extracellular space binds to PATCHED (PTCH1), a 12-pass transmembrane receptor on the surface of cells. Hh binding relieves the inhibitory effect of PTCH1 on Smoothed (SMO), a 7 pass transmembrane domain protein and a member of the G-protein coupled receptor superfamily. Signal transduction by SMO then leads to the activation and nuclear localization of GLI transcription factors and induction of Hh target genes, many of which are involved in proliferation, survival, and differentiation.

A role for aberrant Hh signaling in cancer was initially discovered in patients with Gorlin syndrome, a rare genetic disorder associated with predisposition to BCC, medulloblastoma, and rhabdomyosarcoma. In these patients, mutations in the PTCH1 gene led to ligand-independent activation of SMO and constitutive activity of the Hh pathway (13). Recent molecular and genetic studies have demonstrated that the majority of sporadic human BCCs also have mutations in the Hh signaling pathway, resulting in aberrant activation of the pathway and uncontrolled proliferation of basal cells (14, 15). Two mutations commonly found in BCC result from either the inactivation of the PTCH1 receptor or the activation of SMO protein (16). Both have the same functional consequence, i.e., the uncontrolled activation of the Hh signaling pathway in the absence of the Hh protein. High expression levels of Hh target genes, such as GLI1 and PTCH1, are found in nearly all cases of human BCC examined (17, 18), suggesting that activation of this pathway is a causal event in the initiation of tumor formation. These data suggest that blocking the Hh signaling pathway at the level or downstream of SMO may provide a therapeutic benefit in the treatment of BCC (19).

The feasibility of blocking Hh signaling *in vivo* was first demonstrated as a result of teratogenic phenomena occurring in lambs with mothers that had ingested a particular forage plant, *Veratrum californicum* (20). Cyclopamine, a steroidal alkaloid isolated from this plant, was shown to induce midline deformities, including cyclopia, by blocking SMO signaling in the developing lamb fetuses (21). Cyclopamine has proven to be valuable as a tool compound to confirm the importance of Hh signaling in a subset of malignancies, such as slowing the growth of pancreatic cancer xenografts and blocking the metastatic potential of prostate cancer cells in mice (22, 23).

1.1.2 Vismodegib

Vismodegib (also known as GDC-0449) is a small molecule antagonist of the Hh signaling pathway with a molecular weight of 421.30 g/mol. The International Union of Pure and Applied Chemistry name for vismodegib is 2-chloro-*N*-(4-chloro-3-[pyridin-2-yl]-phenyl)-4-(methanesulfonyl)-benzamide.

Vismodegib binds to and inhibits SMO, thereby preventing the Hh signal. Vismodegib has proven to be efficacious in nonclinical tumor models of both mutated and ligand-overexpressing tumors.

1.1.2.1 Vismodegib Pharmacokinetics

The pharmacokinetics of vismodegib was evaluated in multiple clinical studies in patients with advanced solid tumors, advanced basal cell carcinoma (BCC), and in healthy volunteers.

1.1.2.1.1 Single and Multiple Dose Pharmacokinetics

After a single oral dose, vismodegib demonstrates a unique pharmacokinetic (PK) profile with high, sustained plasma levels and an estimated terminal half-life of 12 days. Parallel concentration–time profiles are observed in the terminal elimination phase

following oral and intravenous (IV) dosing, indicative of elimination rate-limited pharmacokinetics.

After continuous once-daily dosing, steady-state plasma concentrations in patients are typically achieved within approximately 7 days of continuous daily dosing. Increasing the daily dose from 150 mg to 270 or 540 mg does not result in higher steady-state plasma concentrations.

